#### Remote Option for Study Aims:

We have included a description of how each element of the protocol will be administered if remote is necessary.

**Hypothesis:** We hypothesize that the pilot intervention will increase awareness of phthalate chemicals in hair care products and women progressing across the PAPM stages. We expect an inverse association between participants who adopt the use of phthalate-free hair care products and self-reported phthalate-containing hair care products and urinary phthalate concentrations. We compare phthalate concentrations in the 3rd trimester when catabolic activity peaks (Zeng et al. Annals of Nutrition and Metabolism. 2017;70(1):59-65) and subsequently measure sustained behavioral changes 1-month postpartum. We will explore metabolite concentrations across the whole period recognizing the possible limitation of changes in metabolism across the follow-up period.

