## **Specific Aims:**

1. Qualitative Approaches across 5 groups (n=50-100 total participants), we will:

- a. Deliver an educational intervention on harmful chemical exposures, such as phthalates, found in hair care products, developed by the research team using empirical evidence with key informant feedback.
- b. Through focus groups gather participant feedback on content and questions pertaining to intervention and attributes women of color consider when deciding on hair care product use, using a semi-structured guide.

2. Quantitative Approaches using repeat measures, we will:

- a. Using repeated questionnaires to assess PAPM stages, we will assess self-reported behavioral changes in the use of phthalate-free hair care products comparing stage at enrollment to:
  - Stage after the intervention (post-test1),
  - Stage at 1-month post-intervention (post-test2), and
  - Stage at 1-month postpartum (post-test3).
- b. Examine the correlation between self-reported behavioral change assessed by the PAPM questionnaire and
  - Change in self-reported HCP exposure measured via questionnaire (n=50),
  - Change in internal dose of urinary phthalate metabolites (targeted gas chromatography/high resolution mass spectrometry (GC/HRMS) Orbitrap; n=25 with 3-repeat samples),

- (Exploratory) change in internal dose of all-other detectable urinary metabolites (untargeted GC/HRMS-Orbitrap; n=25 with 3-repeat samples).

Questionnaire Constructs : All who wish to enroll and who enroll in the study will be asked to complete the following questionnaires which will be administered preferably via Qualtrix but in paper format if requested.

Eligibility Questionnaire: Confirm that potential participants meet the eligibility requirements (Black or Hispanic women, residing in Northern Manhattan and in the 3rd trimester of pregnancy).

Sociodemographic Questionnaire: Information that includes maternal age, gestational age, race/ethnicity, occupation and educational attainment, and reproductive characteristics and pregnancy details.

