Stage 7: Use phthalate-free HCPs regularly

Research Guides – The Education Intervention Guide and the Focus Group Guide will be developed with the Key Informants and will be submitted for IRB review prior to administration.

Biospecimen Collection, Processing, and Analysis Urine is the preferred biomarker matrix for the hydrophilic phthalate metabolites, whose clearance time is a matter of days and is temporally stable in stored urine samples in spite of their relatively rapid clearance, urine phthalate biomarker measurements are relatively stable over time (days to months); this is likely because exposure sources and patterns of product use are common and fairly consistent. Thus, any changes observed in the urinary metabolites will most likely be due to changes in hair care product practices rather than within-individual variability.

For urine collection, we will follow the CDC urine collection protocol for processing phthalates, and we are asking participants for their first morning urine. Research staff will review the collection procedures with the participants over the phone. Participants will be asked to record date and time of their sample. Urine samples will be stored at or below -20 °C (per the CDC's phthalates urine protocol) within the Biomarkers Core Shared Resource Lab, affiliated with Herbert Irving Comprehensive Cancer Center (Directed by [name]). The urine sample will be assessed for specific gravity to adjust for urine dilution using a refractometer (Adibi JJ, et al. Environ Health Perspect. 2008;116(4):467-473).

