**Phase IV: Educational Intervention and Focus Group Sessions – IN PERSON OR REMOTE**  
Participants will be asked in the welcome letter and reminded during ‘reminder’ calls, emails, and text messages to:

1. Submit completed remote e-consent process to research staff at CUIMC or bring their consent form to an in person session or complete the paper consent form (once received in the mail) and send back to research staff within the prepaid return envelope.
2. Mail in the provided envelope the completed urine kit to the Biomarkers Shared Resource Lab, affiliated with Herbert Irving Comprehensive Cancer Center ([name]) or bring them to an in person meeting.
3. Have completed, via Qualtrics, the questionnaires before the educational intervention.

Based on discussion with the Key Informants, we will do one or a combination of the following for administering the Intervention and Focus Groups REMOTELY:

1. Sessions will be administered consecutively or in two separate sessions to the same group of women. n~50 women with groups of 8-12. Session lasting 1-1.5 hours or 2-2.5 hours, respectively.

2. The intervention session will be administered to n~50 women with groups of 8-12 and the Focus Group Session will be administered to a separate group of n~50 women with groups of 8-12 with each session lasting 1-1.5 hours.

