### **The Educational Intervention:**

The intervention will be followed by a question and answer session. The intervention will focus on phthalate reducing behaviors because of the well documented animal and human evidence on their effects on reproductive health and development, they are ubiquitous and added to HCPs to provide scent, detected in human breast milk, urine, amniotic fluid and placenta (suggesting fetal exposure) and phthalate interventions have proven successful. At the end of the intervention, we will also administer a similar Precaution Adoption Process Model Questionnaire to assess the impact of the intervention.

A trained staff member will prior to the start of the educational intervention if taking place in-person:

1. review the consent form with the participant and obtain written consent before the intervention begins
2. Administer the Sociodemographic Questionnaire (participant self-completes or if preferred, completed with interviewer) before the intervention begins.
3. Administer the Precaution Adoption Process Model Questionnaire (participant self-completes) before the intervention begins.
4. Provide the Hair Care Product Questionnaire to be self-completed if they did not complete the questionnaire prior to the session. Or, provide a return envelope if the participant forgot to bring the completed questionnaire with them.

Remote Option: A trained staff member will have gone over the consent process remotely and will send them links from Qualtrix to complete the Sociodemographic Questionnaire and the Precaution Adoption Process Model Questionnaire prior to the educational intervention.

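### The plan credits urinary metabolite change to hair care product practices, which one uncontrolled group with single voids and a postpartum last sample cannot support

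*Combined protocol and SAP*

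**What the plan says.** The attribution is in Procedures, under Biospecimen Collection, Processing, and Analysis: "any changes observed in the urinary metabolites will most likely be due to changes in hair care product practices rather than within-individual variability". The reason given is that urinary phthalate measurements are fairly stable over days to months, despite a clearance time described with "whose clearance time is a matter of days", because sources and product habits are fairly consistent. No ICC, within-woman SD or coefficient of variation is given.

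The Hypothesis paragraph (under Remote Option for Study Aims) is more careful. It places the phthalate comparison in the 3rd trimester, when catabolic activity is said to peak. It then looks at sustained behaviour 1 month postpartum, and only explores the whole period, "recognizing the possible limitation of changes in metabolism across the follow-up period".

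Aim 2b promises a correlation between self-reported behavioural change and change in urinary phthalate metabolites, with "n=25 with 3-repeat samples". Under Statistical Procedures, Aim 2b Analysis, the Spearman correlations listed are PAPM against change in phthalate-containing products and PAPM against change in PCA patterns. Targeted phthalates get descriptive summaries and a comparison with national levels. The expected results nevertheless include lower MEP.

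**The concern.** The sentence names one preferred cause for any urinary change. At least three other explanations are open in this design: exposure from sources other than hair products, the passage from late pregnancy to postpartum, and ordinary variation between two single voids. If the sentence guides the write-up, a fall in MEP could be reported as evidence that the intervention changed product use when the study cannot tell these explanations apart.

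The analysis that would help most is the association between behavioural change and phthalate change over one interval. Aim 2b promises it, but the analysis section does not specify it for the targeted phthalates.

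**Working it through.** The plan states no figure for this point: no power, effect size, SD or ICC for the urine outcome. The check is therefore first a comparison of the plan's sections, then an illustration on assumed inputs.

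**What the design provides**

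- *Comparator.* Aim 2a reads "we will assess self-reported behavioral changes in the use of phthalate-free hair care products comparing stage at enrollment to" later stages, so each woman is her own control. One remote option says "the Focus Group Session will be administered to a separate group of n~50 women with groups of 8-12", but that group is not described as a control and no urine contrast with it is planned.
- *Samples.* Urine is taken at baseline and at the two follow-ups in Phase V. Three samples over three times is one void per time.
- *Other sources.* Of phthalates, The Educational Intervention says "they are ubiquitous and added to HCPs to provide scent". The Background links personal care products in general to urinary phthalates in pregnancy. Each follow-up collects only the Hair Care Product Questionnaire, the PAPM questionnaire and urine. A change in diet or in non-hair products would go unrecorded.
- *Physiology.* Enrolment is within 0-4 weeks of the 3rd trimester, Follow-Up 1 is mid-late 3rd trimester and Follow-Up 2 is 1 month postpartum. Only the first interval avoids delivery. No analysis step addresses stage of pregnancy.
- *PAPM intervals.* The listed change categories run from pre-test to post-test1, post-test1 to post-test2, post-test2 to post-test3, and post-test1 to post-test3. Pre-test to post-test2 is missing. If post-test2 is the PAPM questionnaire at Follow-Up 1, as the schedule implies, that is the interval matching baseline to Follow-Up 1 urine. Under Metabolomics, the 25 women are prioritised on post-test1 to post-test3 status, a different interval.

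**Random error (assumed: log-concentration SD 0.8 to 1.2, ICC 0.3 to 0.7)**

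SD of a log change between two voids = SD × √(2(1 − ICC)).

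- Favourable end: 0.8 × √0.6 = 0.62. Unfavourable end: 1.2 × √1.4 = 1.42.
- One woman, no true change, 95% range exp(1.96 × SD of change): 3.4-fold to 16.2-fold either way.
- Geometric mean ratio, n=25, 95% factor exp(2.064 × SD of change / 5): 1.29 to 1.80.
- Difference in change between two subgroups, assumed split 12/13, factor exp(2.069 × SD of change × √(1/12 + 1/13)), where the root is 0.400: 1.67 to 3.24.

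**A shift common to all women (assumed: geometric SD 3, ICC 0.4 to 0.8, a 20% fall unrelated to hair products)**

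The SD of change is 1.203 to 0.695, so the standard error at n=25 is 0.241 to 0.139. The log shift is ln 0.8 = −0.223. The chance of an observed mean decline is Φ(0.223/0.241) to Φ(0.223/0.139), about 82% to 95%; a simulation of 20,000 runs gave 82% to 94%. The size and direction of the shift are assumptions. The point is only that a single group cannot separate such a shift from an intervention effect.

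**Precision of the correlation**

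At n=25, with two-sided 5% and 80% power (both assumed), the smallest detectable Spearman correlation is tanh((1.960 + 0.842) × √(1.06/22)) = 0.55.

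**The case against.** The sentence closes a rationale for using urine. It is hedged with a phrase of likelihood, and no analysis applies it. A reader might infer a decision rule that treats metabolite change as product change. The documents contain no such rule: the analysis is called exploratory, and no test of mean urinary change is specified.

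A reader might also infer that rapid clearance and ubiquity contradict the sentence. They do not. The section acknowledges rapid clearance and argues for stability in spite of it, and widespread exposure does not by itself mean that other sources change. The real tension is with the metabolism caveat in the Hypothesis paragraph.

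The plan also has safeguards: first-morning collection, specific-gravity adjustment, a 3rd-trimester comparison placed first, and priority for women who progress or are stagnant. These stand, and they reduce the point. They do not cover unmeasured sources or the postpartum shift, and the 3rd-trimester ordering does not reach the analysis section.

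Finally, the fold ranges describe random error. Within-woman noise widens an interval; it does not bias a mean. That objection stands in full.

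**Conclusion.** The attribution claims more than the design can deliver, and it is not reconciled with the plan's own limitation on metabolism. This follows from the design alone: no comparator, one void per time, no record of non-hair sources at follow-up, and a last sample after delivery. It needs no assumed numbers.

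The figures above rest on an SD, ICC, subgroup split and common shift that are not in the documents. They show how much room chance and a shared shift could occupy. A reader might infer that the urinary results will be biased; the documents show neither that a bias is present nor its direction.

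The point is worth correcting in a pilot because it changes what the urine data can be said to show, and the correction is cheap.

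**What to change.** 1. Replace the attribution sentence. State that overall urinary change is descriptive and may reflect hair product use, other phthalate sources, pregnancy-to-postpartum physiology or within-woman variability.
2. In Aim 2b Analysis, make the main urinary analysis the Spearman correlation between PAPM change and change in specific-gravity-adjusted log MEP from baseline to Follow-Up 1.
3. Define PAPM change over the same interval by adding pre-test to post-test2 to the list of change categories. State that the urine subset is prioritised on post-test1 to post-test3 status, or align that selection.
4. Report change to 1 month postpartum separately, as descriptive, with the metabolism limitation beside it.
5. Describe any contrast of women who progress with women who are stagnant as non-randomised and supportive only. Stagnant women also receive the intervention, and the incentive plan gives everyone a gift card for a phthalate-free product if free samples cannot be obtained. They are not a clean benchmark for within-woman variability.

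This needs no new samples. The costs are a more modest claim, less weight on the postpartum sample, and an internal contrast that is imprecise at n=25: a 95% factor of about 1.67 to 3.24 for a 12/13 split on the assumptions above, against 1.29 to 1.80 for the whole-group mean change.

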#### **Confidentiality:**

All confidential information will remain strictly confidential. The information participants provide in the questionnaires (completed on paper, in person) as well as urine collection receptacles will be assigned a study ID. The urine collection receptacles will have labels with a prepopulated study ID. Each participant study ID will be separated from participant names or any identifiable information. The file that links participant names to Study IDs will be kept in a locked file cabinet and only the investigator and study staff will have access to the file.

The following people and/or agencies will be able to look at, copy, use and share participant research information:

- The principal investigator, Columbia University Medical Center and New York-Presbyterian Hospital study staff and other medical professionals who may be evaluating the study.
- Authorities from Columbia University and New York-Presbyterian Hospital, including the Institutional Review Board ('IRB'). An IRB is a committee organized to protect the rights and welfare of people involved in research.
- The Federal Office of Human Research Protections ('OHRP')

Identifiers might be removed from the identifiable private information or identifiable biospecimens and, after such removal, the information or biospecimens could be used for future research studies without additional consent from participants. Authorization to use and share participant research information does not have an expiration date. Participants have been told that they may change their mind and revoke consent and authorization at any time and for any

reason. They have been instructed to contact the Principal Investigator, whose contact information they have been given, should they decide at any point to revoke consent and authorization.

**Benefit:** There are no direct benefits to participating in this study. **Risk:** This is a minimum risk protocol. Participants may feel anxious by answering some of the questions but they do not have to answer any question that make them feel uncomfortable.

**Retention:** At enrollment, the research staff will complete a participant contact sheet, which includes the subjects' address, home number, cell number, e-mail address, social media information (e.g., Instagram, Facebook), and at least one contact through which the participant can be reached. Additionally, the contact sheet allows documentation of all phone, mail and in-person communication with the study participant. We will also discuss participants' follow-up preferences and safety issues with e-mail or postal mail. For every participant not successfully reached by phone or email, we will mail a letter to her last known address. Even if a participant has moved, mail is often forwarded to the new address.

Participants will be contacted via phone (call or text) and/or e-mail two to four days prior to the educational intervention/focus group session. Should a participant miss their session, we will follow-up via phone, mail, or email. If unable to contact during the follow-up period, we will also additionally contact participants through social media (direct message) (with permission) or through the alternative contact the participant provided upon enrollment. In addition, participants will have monthly check-ins through phone, mail, and/or e-mail.

**Incentives:** We will provide study participants a \$40 Target gift card incentive per session (\$20 Target gift card for urine sample submission and \$20 Target gift card per questionnaire completed) and have budgeted an additional \$20 per attendee to cover the cost of refreshments served at the educational intervention and to reimburse for up to \$20 worth of travel to and from Columbia University (if in-person). If sessions are conducted remotely, participants will not be reimbursed for travel expenses. Additionally, we are looking to acquire free hair product samples from Shea Moisture, but in case they are not available, we will provide everyone with \$10 Target gift cards to purchase a phthalate-free product from Target.

The Target Gift Card incentive structure will be a phased-out incentive system that will no longer be used where the new CUIMC Human Subject Clinical Trial participants Prepaid Visa Debit Cards will now be the default for providing compensation. Each participant will receive one card through the mail. Once the participant verifies that they have received the card, they can activate the card. Once the card is activated, each participant will begin to access funds that are pushed to their visa card as an incentive to study participation. The same amount of incentive per study part completion as described above will be provided. The participants will now have the flexibility of use outside of Target and eliminates multiple transactions per participant follow-up. If a visa card is lost, the card will be deactivated. If the visa card is lost with funds remaining on the visa card, the participant will contact the bank and study staff to go through the process of issuing a new card. We will abide by all policies that are in accordance with this CUIMC Incentive system.

We aim to make the Prepaid Visa incentive system the default incentive system beginning October 2021. The Prepaid Visa Registration System is an approved system for research participants through CUIMC. All currently enrolled participants will be re-consented using the updated consent form to this payment structure.

**Phase III: Sending Study Materials Prior to the In-Person or Remote Session** We are asking enrolled participants to consent to send the following items to their mailing address, email address, and text message link to cell phone prior to their in-person session (when applicable): the consent form, the Hair Care Product Questionnaire, and the urine sample collection kit (with icepack). Please see Consent Form for more details. In brief, once determined eligible, a trained study team member will email or text a link to the remote e-consent process and review the information with the participant over the phone to answer any questions they may have. Part of this process includes asking the participant for verbal consent to send the aforementioned items to a mail and email address of the participants choosing, as well as text message links. The participant will complete the remote e-consent process this same way. The Hair Care Product Questionnaire provided via Qualtrix is best to be completed in the space where the woman conducts her everyday hair care routine as she will need to recall product type and name. We are also asking for first morning urine to standardize collection of all urine samples over time.

In the case we do not get verbal consent to provide study materials using any of these methods, it will be difficult for them to participate in this study remotely. Therefore, we will then say during the consent process “If and when this study has an in-person component, could we contact you in the future?” and provide Yes and No options.

**Phase IV: Educational Intervention and Focus Group Sessions – IN PERSON OR REMOTE**  
Participants will be asked in the welcome letter and reminded during ‘reminder’ calls, emails, and text messages to:

1. Submit completed remote e-consent process to research staff at CUIMC or bring their consent form to an in person session or complete the paper consent form (once received in the mail) and send back to research staff within the prepaid return envelope.
2. Mail in the provided envelope the completed urine kit to the Biomarkers Shared Resource Lab, affiliated with Herbert Irving Comprehensive Cancer Center ([name]) or bring them to an in person meeting.
3. Have completed, via Qualtrics, the questionnaires before the educational intervention.

Based on discussion with the Key Informants, we will do one or a combination of the following for administering the Intervention and Focus Groups REMOTELY:

1. Sessions will be administered consecutively or in two separate sessions to the same group of women. n~50 women with groups of 8-12. Session lasting 1-1.5 hours or 2-2.5 hours, respectively.

2. The intervention session will be administered to n~50 women with groups of 8-12 and the Focus Group Session will be administered to a separate group of n~50 women with groups of 8-12 with each session lasting 1-1.5 hours.

